In a 24-hour recall method, individuals are asked to provide detailed information about all foods and beverages consumed in the previous 24 hours (Meijboom, 2017). To obtain a reliable estimate of habitual dietary intake, the 24-hour recall must be repeated on multiple days in order to correct for day-to-day variation. Wageningen University & Research has developed and validated a Dutch online 24-hour dietary recall method that can be completed entirely online by participants, known as “Compl-Eat” (Meijboom, 2017). This significantly reduces the costs and burden for both researchers and participants.

This study will consist of two phases. The first phase will involve a pre-test to assess the usability, comprehensibility, and completeness of the developed Nutri+ module among end users and experts. The insights generated will be used to further improve the Nutri+ module and the profile wheel visualization. After completion of the first phase, the second phase will commence, in which the Nutri+ module will be compared with a reference method in an evaluation study. The selected reference method for this evaluation study is a 24-hour recall using Compl-Eat.

2 Goal

Goal of the Nutri+ module: To assess, at the individual level, the extent to which a person complies with the dietary guidelines and where there is room for improvement. These insights are used to provide personalized dietary advice and to monitor an individual's dietary intake.

Phase 1: Pre-test

Objectives

- To gain insight into the user experiences of the target group with completing the questionnaire and with regard to the visualization of the profile wheel.
- To collect feedback from experts on the Nutri+ module (including completeness, question formulation, example products, etc.).
- To use the collected user insights and expert feedback to further improve the Nutri+ module and the profile wheel visualization before starting the second phase of the study (the evaluation study).

Phase 2: Evaluation study

Main objective: To evaluate whether the absolute intake in grams, as measured by the Nutri+ module, is comparable to Compl-Eat for the 21 product groups. This will be explored both quantitatively (e.g., what percentage of intake is covered by the Nutri+ module compared with Compl-Eat) and qualitatively (e.g., where the differences between Compl-Eat and the Nutri+ module lie). These insights can be used to further improve the tool.

Sub-objectives:

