After completing the first series (autumn 2022), participants are reminded that they will be contacted again in spring 2023 to complete the Nutri+ module and Compl-Eat. The same procedures are followed in spring 2023 as in autumn 2022.

Participants are also asked to complete an evaluation questionnaire regarding their experiences with completing the questionnaire and the visualization of the dietary profile wheel.

After data collection for the evaluation study is completed, the data are analyzed. Based on this analysis, recommendations will be made for adjusting the Nutri+ module (questionnaire, algorithms, and cut-off values) and for improving the visualization of the profile wheel.

Tabel 2: Overview timeline and investment for participants evaluation study

	How often and when	Total time investment
--	--------------------	-----------------------

Nutri+ module	1 time filling out autumn 2022 1 time filling out spring 2023	2 times, 20 minutes. 40 minutes in total.
Compl-eat	1 time 4 days filling out autumn 2022 1 time 4 days filling out spring 2023	80 minutes per time. 160 minutes in total.
Evaluation questionnaire	1 time filling out	15 minutes

6 Outcome variables

To evaluate the Nutri+ module in comparison with Compl-Eat, it is first necessary to assess the extent to which the food groups used in the Nutri+ module are also available in Compl-Eat. The outcomes listed below depend on the results of this mapping. In addition, Compl-Eat will need to apply the same food group classification based on the same cut-off values per product group as used in the Nutri+ module.

Primary outcomes

- Intake in grams for the 17 product groups that are quantitatively assessed (Fruit, Vegetables, Legumes, Nuts and Seeds, Fish, Dairy, Meat, Eggs, Soft Drinks, Alcohol, Coffee, Tea, Snacks, Sweet Spreads, Chips/Nuts/Party Snacks, Fast Food, Desserts/Ice Cream/Cakes) for both Compl-Eat and the Nutri+ module.

Secondary outcomes

- Evaluation overall and by subgroup (sex, BMI, etc.) for all product groups available in both Compl-Eat and the Nutri+ module, for which guidelines exist to assess reproducibility and classification. For Nutri+, these include: Fruit, Vegetables, Butter and Cooking/Frying Products, Dressings and Oils, Legumes, Nuts and Seeds, Fish, Dairy, Meat, Eggs, Cereal Products, Potatoes, Soft Drinks, Alcohol, Coffee, Tea, Snacks, Sweet Spreads, Chips/Nuts/Party Snacks, Fast Food, Desserts/Ice Cream/Cakes.
- Energy intake based on Compl-Eat

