- Expected energy intake based on sex, age, weight, and physical activity
- Evaluation of the profile wheel

7 Description of incidents, safety, adverse events, side effects

The study for participants consists of completing dietary questionnaires and 24-hour dietary recalls. Due to the nature of the study, no incidents or adverse events are expected. Any complaints regarding the conduct of the study, the websites used, or other questions or remarks can be submitted via email or telephone, as indicated in the participant information.

8 Data-analysis and statistics

For Compl-Eat, all analyses will be based on the average intake per product group across the four assessment days within a single measurement series (spring or autumn).

Based on the Compl-Eat data, it will be assessed whether there is excessive under- or over-reporting in the study population. To this end, the number of calories consumed, as calculated by Compl-Eat, will be compared with the expected caloric intake based on participants' age, sex, height, and weight.

The agreement between classifications in Compl-Eat and the Nutri+ module will be evaluated by assessing the percentage overlap in categorization and subsequently examining correlations between the scores. The goal is for 75% agreement per product group between the Nutri+ module and Compl-Eat. If lower agreement is observed, the data will be qualitatively examined to identify areas for improvement in the Nutri+ module.

In addition, the intake in grams per product group as measured by the Nutri+ module and Compl-Eat will be examined. Correlation coefficients will be calculated to assess agreement between the Nutri+ module and Compl-Eat. These outcomes are primarily exploratory and aim to provide insight into where the largest differences between Compl-Eat and Nutri+ occur. These insights can be used to further improve the Nutri+ module.

To assess the reproducibility of the Nutri+ module, correlations between the spring and autumn measurements will be used.

Participants' opinions on the visualization of the profile wheel will be evaluated using descriptive information.

9 Risk analysis relating to the conduct of the study

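### Comparability of grams is the main objective, but the only agreement statistic named for grams is a correlation, which does not register bias

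*Combined protocol and SAP*

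**What the plan says.** Section 2 gives the Phase 2 main objective as: "To evaluate whether the absolute intake in grams, as measured by the Nutri+ module, is comparable to Compl-Eat for the 21 product groups". It adds that this will be explored quantitatively and qualitatively, with one quantitative example: "what percentage of intake is covered by the Nutri+ module compared with Compl-Eat". The primary outcome in Section 6 is "Intake in grams for the 17 product groups that are quantitatively assessed", for both methods. (The difference between 21 and 17 groups is a separate matter.)

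On grams, Section 8 says three things:

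- A general statement: "the intake in grams per product group as measured by the Nutri+ module and Compl-Eat will be examined".
- One named statistic: "Correlation coefficients will be calculated to assess agreement between the Nutri+ module and Compl-Eat".
- A purpose: "These outcomes are primarily exploratory and aim to provide insight into where the largest differences between Compl-Eat and Nutri+ occur".

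Two other planned analyses bear on the point. For the red, orange and green categories, "The goal is for 75% agreement per product group between the Nutri+ module and Compl-Eat", with a qualitative look at the data where agreement is lower. And "Based on the Compl-Eat data, it will be assessed whether there is excessive under- or over-reporting in the study population", by comparing calories from Compl-Eat with expected calories.

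**The concern.** A question about absolute grams is a question about the size of the difference between two methods. A correlation answers a different question: whether people who score high on one method also score high on the other. If Nutri+ recorded half of everyone's Compl-Eat intake, the two methods would not be comparable in grams, and the correlation would not show it.

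For the same reason, correlation cannot serve the purpose that Section 8 itself states. Ordering product groups by correlation does not order them by size of difference. Section 5 says the analysis will lead to recommendations on the questionnaire, algorithms and cut-off values. Changing cut-offs needs the direction and size of bias for each group, and no planned statistic is specified to supply them.

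**Working it through.** The documents give no SD, margin or sample-size calculation for the gram comparison, so there is no stated figure to reproduce. The check has four parts.

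**1. Invariance.** Let X be Compl-Eat grams and Y be Nutri+ grams. For any shift a and any factor b > 0,

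corr(X, a + bY) = b·cov(X, Y) / (SD(X)·b·SD(Y)) = corr(X, Y).

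Ranks do not change either, so Spearman's coefficient is also fixed. This needs no assumption about intake.

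**2. Illustration.** Assumed: both methods have mean 150 g and SD 75 g before bias, with r = 0.6; 200,000 simulated pairs. Lin's concordance = 2cov / (var₁ + var₂ + (difference in means)²).

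| Nutri+ | Pearson | Spearman | Mean difference (g) | 95% limits of agreement (g) | Lin's concordance |
|---|---|---|---|---|---|
| unbiased | 0.602 | 0.580 | 0 | −131 to 131 | 0.60 |
| × 0.7 | 0.602 | 0.580 | −45 | −163 to 73 | 0.46 |
| × 0.5 | 0.602 | 0.580 | −75 | −193 to 43 | 0.27 |
| −50 g | 0.602 | 0.580 | −50 | −181 to 81 | 0.49 |

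The pattern is the same at r = 0.4 (Pearson 0.400 in every row) and r = 0.8 (0.799 in every row).

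**3. Would the 75% category check catch the bias?** The introduction puts the colour cuts at roughly 100% and 50% of the recommended amount. Assumed: log-normal intake with log-SD 0.4 and median at the guideline, no measurement error, and Nutri+ = c × Compl-Eat. In units of the guideline, for 0.5 ≤ c < 1 the colour changes when intake lies in [1, 1/c) or [0.5, 0.5/c).

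For c = 0.85:
- [1, 1.176): z from 0 to 0.406, probability 0.158.
- [0.5, 0.588): z from −1.733 to −1.327, probability 0.051.
- Same colour: 1 − 0.158 − 0.051 = 0.79.

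For c = 0.8:
- [1, 1.25): z from 0 to 0.558, probability 0.212.
- [0.5, 0.625): z from −1.733 to −1.175, probability 0.078.
- Same colour: 1 − 0.212 − 0.078 = 0.71.

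| c | 0.85 | 0.8 | 0.7 | 0.6 | 0.5 |
|---|---|---|---|---|---|
| Same colour | 79% | 71% | 53% | 32% | 8% |
| Reaches 75% | yes | no | no | no | no |

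The correlation is 1.00 in every column. On the other side, a uniform 25% overestimate (c = 1.25) gives 76% and passes. The result also depends on where intake lies relative to the guideline. With the median at twice the guideline, c = 0.7 gives 84%; with the median at 0.3 of the guideline, c = 0.5 gives 90%. Both pass.

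**4. Can the planned sample estimate bias?** Let SDd be the SD of the paired differences, with one difference per participant. The 95% CI half-widths are t·SDd/√n for the bias and t·SDd·√(1/n + 1.96²/(2(n−1))) for each limit of agreement. At n = 200 (t = 1.972):

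- Bias: 1.972/√200 = 0.14 SDd.
- Limit: 1.972·√(0.00500 + 0.00965) = 0.24 SDd.

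At n = 150 these are 0.16 and 0.28; at n = 300, 0.11 and 0.19. In the × 0.7 row above, SDd = 75·√(1 + 0.49 − 2·0.6·0.7) = 60.5 g, so the bias of −45 g would have a 95% CI of about ±0.139 × 60.5 = ±8.4 g.

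**The case against.** The plan is less bare than a quick reading suggests. Section 8 says that grams from both methods will be looked at to find the largest differences, and Section 2 names percentage coverage. Some description of bias is therefore intended. Section 2 also presents the main objective as something to be explored, so calling the gram analysis primarily exploratory in Section 8 is consistent with it. And the 75% category check reacts to bias: it would flag every uniform underestimate of 20% or more in the median-at-guideline model above. All of this stands, and it limits the point.

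It does not remove it. Neither the general statement nor the coverage example comes with a measure, an interval or a method. The category check serves a sub-objective, does not express anything in grams, lets moderate bias pass, and says nothing about groups without a guideline, which the introduction says are shown in grey. The under- and over-reporting check uses Compl-Eat energy only and does not involve Nutri+ grams. An absolute-agreement intraclass correlation or Lin's concordance would react to bias, but Section 8 names neither.

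**Conclusion.** The point holds. For the main objective and primary outcome, the only named agreement statistic cannot detect a shift or rescaling of grams, so it cannot show comparability or locate the largest differences. The invariance is exact. The gram figures and colour percentages rest on the stated assumptions, including a single 50%/100% colour rule; the documents do not show how the cuts work for groups such as soft drinks, alcohol or snacks.

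Three stronger readings are tempting, and the documents do not support them:

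- *Correlation is the only gram analysis.* It is the only named statistic; an unspecified look at the grams is also planned.
- *A high correlation would count as a pass.* No threshold is set for the correlation between Nutri+ and Compl-Eat. The 0.75 criterion in Section 2 applies to reproducibility of Nutri+ over time.
- *Bias large enough to change everyone's colour would go unnoticed.* Even at c = 0.5, 8% keep their colour in this model, and the 75% check would flag that case.

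The consequence is an incomplete answer to the main objective, with a ranking measure labelled as agreement. Section 8 should be corrected before the gram data are analysed.

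**What to change.** In Section 8, for each of the 17 gram outcomes:

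- Make the main analysis the paired difference, Nutri+ minus Compl-Eat, within a measurement series. Report mean (or median) bias with 95% CI and Bland-Altman limits of agreement.
- Use regression-based limits where spread grows with the mean, and percentile-based limits for skewed or zero-heavy groups. Use the log scale only where there are no zeros. Four-day means may well contain many zeros for groups such as fish, legumes or alcohol.
- Report coverage as the ratio of group means with 95% CI. Individual ratios fail when Compl-Eat is zero.
- Keep correlation as a secondary measure of ranking, and delete the words *to assess agreement* from that sentence.
- State that limits against a four-day mean include day-to-day variation in Compl-Eat, so wide limits cannot be read as Nutri+ error alone.
- If a yes/no conclusion on comparability is wanted, set an acceptable difference in advance. Otherwise, report bias and limits as estimates.

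The cost is revised wording and a few more tables and plots from data the study already collects. The results will probably look less favourable than correlations.

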- To investigate whether the results of the Nutri+ module are reproducible over time or whether time effects are present, with a correlation coefficient of ≥ 0.75 between two measurement points considered successful.
- To evaluate the Nutri+ module (dietary questionnaire) against the Compl-Eat 24-hour recall method. Specifically, we aim to examine whether the Nutri+ module can accurately classify at least 75% of individuals into three categories for the 21 product groups.
- To evaluate the visualization of the profile wheel by users of the Nutri+ module.

3 Study design

This is a longitudinal randomized study to evaluate the Nutri+ dietary intake module. The Nutri+ module can be completed by participants at home via an online portal; it is filled out only once and takes approximately 30 minutes to complete. As a reference method, Compl-Eat is used. This is an online 24-hour recall method developed by Wageningen University & Research (Meijboom et al., 2017). Participants in the study can complete this 24-hour recall themselves at home via a portal, recording everything they ate and drank in the previous 24 hours. Based on the submitted data, the Compl-Eat platform can determine for an individual how much and what was consumed at both the product group and individual product levels. Compl-Eat is completed by participants on four non-consecutive days—three weekdays and one weekend day (Saturday or Sunday)—to obtain an accurate representation of an individual's average intake. The 24-hour recalls are manually checked for completeness by a researcher afterwards.

A randomized cross-over design is used, in which one group of participants completes the Nutri+ module first, while the other group completes Compl-Eat first. The days on which participants complete

the Nutri+ questionnaire and the days on which Compl-Eat is completed are randomly selected. There is a minimum interval of 7 days between the Nutri+ module and the first or last day of Compl-Eat.

In addition, possible time effects in dietary recording and the reproducibility of the Nutri+ module results are examined. To this end, participants are invited again after three to six months to repeat the entire procedure of completing the Nutri+ module once and Compl-Eat four times. The first series of questionnaires is sent out in April; the second series begins in September.

See Figure 2 for a schematic overview of the study design.

[figure not shown]

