The second phase involves recruiting participants through social media campaigns and the completion of the Nutri+ module and Compl-Eat. Participants are recruited via social media advertisements, which link them to an online information sheet. After reading the information sheet, participants can provide online informed consent for participation in the study. They are then automatically directed to an online screening questionnaire (see inclusion and exclusion criteria). This screening questionnaire automatically assesses whether the individual meets the study's selection criteria. Candidates who do not meet the criteria are informed immediately. Candidates who do meet the criteria are directed to a baseline questionnaire to collect various baseline data (medication use, physical activity, adherence to any dietary or nutritional rules, and allergies or intolerances). Participants are then informed about the further study schedule and procedures.

The study uses a cross-over design, in which participants are randomly assigned to one of two sequences: starting with the Nutri+ module or starting with Compl-Eat. Participants who start with the Nutri+ module during the first series (autumn 2022) will start with Compl-Eat during the second series (spring 2023), and vice versa.

For all participants, the days on which the Nutri+ module and Compl-Eat must be completed are randomly selected. Both the Nutri+ module and Compl-Eat are completed at home using login credentials for the respective online platforms. Participants are not informed of the full schedule in advance to minimize potential influence on their dietary behavior. One day before a participant's first "assessment day," they are contacted by email by a researcher, requesting that they complete either the Nutri+ module or Compl-Eat the following day. Participants can respond to this email if the scheduled day does not fit their personal planning. In that case, the researcher reschedules the assessment day, and the participant is contacted again at a later time.

During the first series (autumn 2022), all participants complete Compl-Eat on four days within a two-week period and complete the Nutri+ module once. A minimum interval of seven days is maintained between completing Compl-Eat and the Nutri+ module to prevent interference between the methods.

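### Time effects in Nutri+ are judged only by a spring–autumn correlation of at least 0.75, which misses a group-level shift, and the documents reverse the order of the two series

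*Combined protocol and SAP*

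**What the plan says.** One sub-objective of the evaluation study (Section 2) is "To investigate whether the results of the Nutri+ module are reproducible over time or whether time effects are present". The only rule attached to it is "with a correlation coefficient of ≥ 0.75 between two measurement points considered successful". Section 3 restates the aim: "possible time effects in dietary recording and the reproducibility of the Nutri+ module results are examined".

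The matching analysis in Section 8 is a single sentence: "To assess the reproducibility of the Nutri+ module, correlations between the spring and autumn measurements will be used". The section does not say whether Pearson, Spearman or an intraclass coefficient is meant. It plans no between-series mean difference, limits of agreement or model of change. Compl-Eat is repeated in both series and averaged within each, but Section 8 does not use it to interpret change in Nutri+.

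On timing, Section 3 says "participants are invited again after three to six months to repeat the entire procedure" and "The first series of questionnaires is sent out in April; the second series begins in September". Section 5 (Second Phase) describes participants who begin with Nutri+ "during the first series (autumn 2022) will start with Compl-Eat during the second series (spring 2023". It repeats that order when describing the reminder to participants, and Table 2 lists the seasons in the same order.

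**The concern.** The sub-objective has two parts: stability of the results and presence of a time effect. The only planned statistic speaks to the first. If all participants report more, or less, of a product group in the second series, an ordinary correlation is unchanged and the criterion is met.

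This matters because absolute level is what the tool uses. Nutri+ assigns red, orange or green by comparing intake with fixed guideline amounts, and one of its stated purposes is to monitor an individual's intake. A stable ranking with a shifted level would change the colours people see.

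A low correlation is also hard to read. Both stated calendars pair one spring with one autumn measurement, so real change in a person's diet lowers the correlation just as instrument error does. The 0.75 rule is the only pass/fail standard for reproducibility, and Section 5 says the results will guide changes to the questionnaire, algorithms and cut-offs.

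**Working it through.** **Inputs from the documents.** Threshold 0.75 (Section 2); recruitment target 200, up to 300 (Section 4); retest window three to six months, April then September (Section 3); autumn 2022 then spring 2023 (Section 5, Table 2). The 0.75 is a chosen threshold and 200 comes without a calculation, so the plan has no computed figure to reproduce.

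**Assumptions, not in the documents.** True correlation 0.80; equal SD in both series; the shifts, reliabilities and between-season correlations shown below.

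**1. Group-level shift.** With a uniform shift of d SDs and equal variances, Pearson r is unchanged and the absolute-agreement ICC is r / (1 + d²/2).

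| Shift d | r | ICC |
|---|---|---|
| 0 | 0.80 | 0.80 |
| 0.25 | 0.80 | 0.80 / 1.03125 = 0.78 |
| 0.5 | 0.80 | 0.80 / 1.125 = 0.71 |
| 1.0 | 0.80 | 0.80 / 1.5 = 0.53 |

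A simulation gave the same values to within 0.001. Multiplying all second-series values by 1.5 also left r at 0.80. Spearman is equally blind to any change that preserves rank order.

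The planned data could show such a shift. The SE of the paired mean change, in SD units, is √(2(1 − r)/n). With r = 0.80 and 200 complete pairs this is √(0.4/200) = 0.0447, so a 0.25 SD shift gives z = 0.25 / 0.0447 = 5.6. With only 100 complete pairs, z = 0.25 / 0.0632 = 4.0.

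**2. Person-level change.** The expected observed r is instrument reliability × true between-season correlation of intake. It falls below 0.75 once the true correlation is below 0.75 / reliability:

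- reliability 0.80: 0.75 / 0.80 = 0.94
- reliability 0.85: 0.75 / 0.85 = 0.88
- reliability 0.90: 0.75 / 0.90 = 0.83

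The outcome depends on the inputs. At reliability 0.85, a true correlation of 0.80 gives 0.68 (fail) and 0.90 gives 0.765 (pass).

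**3. Precision.** The 95% interval for an observed r of 0.75 is tanh(atanh 0.75 ± 1.96/√(n − 3)). This gives 0.68 to 0.81 with 200 complete pairs (0.682 to 0.805) and 0.67 to 0.81 with 160. The plan does not say how this uncertainty enters the judgement.

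**4. Calendar.** April to September is 4.1 to 6.0 months depending on the days, within the stated window. Section 5 gives seasons only. Taking autumn as September–November and spring as March–May (an assumption), the interval is about 3.0 to 8.9 months.

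**The case against.** - **The coefficient is unnamed.** If an absolute-agreement ICC were meant, a mean shift would show. That is true, but nothing in the documents says so, and both Section 2 and Section 8 speak only of correlation.
- **A correlation does see some time effects.** This stands. A reader might infer that it cannot detect any. It is blind to a group-level shift or rescaling, but change that differs between people lowers it.
- **A shift could surface elsewhere.** Percentage coverage against Compl-Eat and three-category agreement both depend on absolute level, so a shift in Nutri+ alone might appear there. However, no between-series contrast of these is planned, so they do not fill the gap in the reproducibility criterion.
- **The interval may be within the window.** A reader might put Section 3's months into Section 5's order and infer a seven-month retest outside the window. The documents do not support this, because Section 5 names no months and November to March, for example, is four months. What they do support is that the order is reversed.
- **A reliable tool need not fail.** The calculations above show both outcomes under plausible assumptions. They show that a low r is ambiguous. They do not show that failure is expected.
- **Comparing mean change between methods does not separate person-level seasonal change from instrument error.** This stands, and an ICC across seasons mixes the two as well. The remedy has to say so.

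**Conclusion.** The concern holds for the reproducibility sub-objective. As written, the plan could declare success despite a sizeable group-level time effect. At an assumed r of 0.80 with equal variances, a 0.5 SD shift takes absolute agreement to 0.71 and a 1 SD shift to 0.53, with r still at 0.80. In the other direction, for assumed reliability between 0.80 and 0.90, the criterion is missed once the true between-season correlation drops below 0.94 to 0.83, so a low value is not by itself evidence against the tool.

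The contradiction in series order rests on no assumption. It does not alter the statistical point, since either version compares a spring with an autumn measurement, but the retest interval behind the criterion is undetermined until it is resolved.

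This should be fixed, but a reader should not infer that it undermines the study. The main objective, gram intake against Compl-Eat, does not rest on this criterion.

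**What to change.** In Section 8:

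- Report, per product group, the paired mean change in Nutri+ between series with its 95% confidence interval. This answers the time-effects question.
- Report an absolute-agreement ICC with its 95% confidence interval, and apply the 0.75 criterion to that ICC.
- Report the same mean change and the between-series correlation for Compl-Eat, plus the method-by-series interaction. Treat these as context: group-level change shared by both tools points to diet or season, while change in one tool only points to possible reporting drift in that tool.
- State the limits: this does not separate person-level seasonal change from instrument error, and four recall days are a noisy reference for rarely eaten groups such as fish or legumes.

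In Sections 3 and 5 and Table 2, reconcile the order of the series to one calendar and restate the retest interval it gives.

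The cost is a little more analysis of measurements already planned, plus text changes. The criterion also becomes harder to meet when there is a shift, because the ICC then lies below the correlation. At r = 0.80 it reaches 0.75 at a shift of √(2 × (0.80/0.75 − 1)) = 0.37 SD. A genuine seasonal change in mean intake would lower it too, which is why the Compl-Eat change should be read beside it.
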